9.7.4 Other Statistical/Analytical Issues

Adaptive Randomization in the MCI/Prodromal Cohort

Randomization to placebo or 1 of 3 dose groups of E2609 will be fixed for the first 100 MCI/Prodromal subjects randomized in the study (1:1:1:1; placebo to each of the 3 active doses for the first 100 MCI/Prodromal subjects randomized, including those randomized from both Stage A and Stage B). Thereafter, randomization probabilities to each treatment group will be updated at each interim analysis, such that the randomization probability will be increased for the placebo group and dosage groups that represent the potential target dose (ED₉₀), and simultaneously decreased for other active arms. (revised per Amendment 01)

Randomization in the Mild to Moderate AD Cohort (revised per Amendment 01)

In Stage A, the mild to moderate AD subjects will be randomized to placebo or 1 of 3 E2609 dose groups (5, 15, and 50 mg of E2609) at a 1:1:1:1 ratio, while in Stage B, the mild to moderate AD subjects will be randomized to placebo or 1 of 2 E2609 dose groups (15 and 50 mg E2609) at a 1:1:1 ratio. (revised per Amendment 01)

Stratification (revised per Amendment 01)

Within the 2 clinical cohorts (MCI/Prodromal and mild to moderate AD), subjects will be stratified at randomization by *ApoE4* status (positive or negative) and prior treatment with AChEIs or memantine or both (yes or no). (revised per Amendment 01)

9.7.5 Procedure for Revising the Statistical Analysis Plan

If the statistical analysis plan needs to be revised after the study starts, the sponsor will determine how the revision impacts the study and how the revision should be implemented. The details of the revision will be documented and described in the clinical study report.

11 PROCEDURES AND INSTRUCTIONS (ADMINISTRATIVE PROCEDURES)

11.1 Changes to the Protocol

Any change to the protocol requires a written protocol amendment or administrative change that must be approved by the sponsor before implementation. Amendments specifically affecting the safety of subjects, the scope of the investigation, or the scientific quality of the study require submission to health or regulatory authorities as well as additional approval by the applicable IRBs/IECs. These requirements should in no way prevent any immediate action from being taken by the investigator, or by the sponsor, in the interest of preserving the safety of all subjects included in the study. If the investigator determines that an immediate change to or deviation from the protocol is necessary for safety reasons to eliminate an immediate hazard to the subjects, the sponsor's medical monitor and the IRB/IEC for the site must be notified immediately. The sponsor must notify the health or regulatory authority as required per local regulations.

Protocol amendments that affect only administrative aspects of the study may not require submission to health or regulatory authority or the IRB/IEC, but the health or regulatory authority and IRB/IEC (or if regionally required the head of the medical institution) should be kept informed of such changes as required by local regulations. In these cases, the sponsor may be required to send a letter to the IRB/IEC and the Competent Authorities (or, if regionally required, the head of the medical institution) detailing such changes.

11.2 Adherence to the Protocol

The investigator will conduct the study in strict accordance with the protocol (refer to ICH E6, Section 4.5).

11.3 Monitoring Procedures

The sponsor's or CRO's CRA will maintain contact with the investigator and designated staff by telephone, letter, or email between study visits. Monitoring visits to each site, and potential remote source document verification, will be conducted by the assigned CRA as described in the monitoring plan. The investigator (or if regionally required, the head of the medical institution) will allow the CRA to inspect the clinical, laboratory, and pharmacy facilities to assure compliance with GCP and local regulatory requirements. The eCRFs and subject's corresponding original medical records (source documents) are to be fully available for review by the sponsor's representatives at regular intervals. These reviews verify adherence to study protocol and data accuracy in accordance with local regulations. All records at the site are subject to inspection by the local auditing agency and to IRB/IEC review.

In accordance with ICH E6, Section 1.52, source documents include, but are not limited to, the following:

- Clinic, office, or hospital charts
- Copies or transcribed health care provider notes that have been certified for accuracy after production
- Recorded data from automated instruments such as IxRS, x-rays, and other imaging reports (eg, sonograms, computed tomography scans, MRIs, radioactive images, ECGs, rhythm strips, electroencephalography, polysomnographs, pulmonary function tests) regardless of how these images are stored, including microfiche and photographic negatives
- Pain, quality of life, or medical history questionnaires completed by subjects
- Records of telephone contacts
- Diaries or evaluation checklists
- Drug distribution and accountability logs maintained in pharmacies or by research personnel
- Laboratory results and other laboratory test outputs (eg, urine pregnancy test result documentation and urine dip-sticks)
- Correspondence regarding a study subject's treatment between physicians or memoranda sent to the IRBs/IECs
- CRF components (eg, questionnaires) that are completed directly by subjects and serve as their own source

11.4 Recording of Data

An eCRF is required and must be completed for each subject by qualified and authorized personnel. All data on the eCRF must reflect the corresponding source document, except when a section of the eCRF itself is used as the source document. Any correction to entries made on the eCRF must be documented in a valid audit trail where the correction is dated, the individual making the correction is identified, the reason for the change is stated, and the original data are not obscured. Only data required by the protocol for the purposes of the study should be collected.

The investigator must sign each eCRF. The investigator will report the eCRFs to the sponsor and retain a copy of the eCRFs.

11.5 Identification of Source Data

All data to be recorded on the eCRF must reflect the corresponding source documents.

11.6 Retention of Records

The circumstances of completion or termination of the study notwithstanding, the investigator (or if regionally required, the head of the medical institution or the designated representative) is responsible for retaining all study documents, including but not limited to the protocol, copies of eCRFs, the Investigator's Brochure, and regulatory agency registration documents (eg, Form FDA 1572, ICFs, and IRB/IEC correspondence). The site should plan to retain study documents, as directed by the sponsor, for at least 2 years after the last approval of a marketing application in an ICH region and until there are no pending or contemplated marketing applications in an ICH region or at least 3 years have elapsed since the formal discontinuation of clinical development of the investigational product.

It is requested that at the completion of the required retention period, or should the investigator retire or relocate, the investigator contact the sponsor, allowing the sponsor the option of permanently retaining the study records.

11.7 Auditing Procedures and Inspection

In addition to routine monitoring procedures, the sponsor's Clinical Quality Assurance department conducts audits of clinical research activities in accordance with the sponsor's standard operating procedures to evaluate compliance with the principles of ICH GCP and all applicable local regulations. If a government regulatory authority requests an inspection during the study or after its completion, the investigator must inform the sponsor immediately.

11.8 Handling of Study Drug

All study drug will be supplied to the principal investigator (or a designated pharmacist) by the sponsor. Drug supplies must be kept in an appropriate secure area (eg, locked cabinet) and stored according to the conditions specified on the drug labels. The investigator (or a designated pharmacist) must maintain an accurate record of the shipment and dispensing of the study drug in a drug accountability ledger, a copy of which must be given to the sponsor at the end of the study. An accurate record of the date and amount of study drug dispensed to each subject must be available for inspection at any time. The CRA will visit the site and review these documents along with all other study conduct documents at appropriate intervals once study drug has been received by the site.

All drug supplies are to be used only for this study and not for any other purpose. The investigator (or site personnel) must not destroy any drug labels or any partly used or unused drug supply before approval to do so by the sponsor. At the conclusion of the study and as appropriate during the study, the investigator (or a designated pharmacist) will return all used and unused drug containers, drug labels, and a copy of the completed drug disposition form to the sponsor's CRA (or designated contractor).

11.9 Publication of Results

All manuscripts, abstracts, or other modes of presentation arising from the results of the study must be reviewed and approved in writing by the sponsor in advance of submission pursuant to the terms and conditions set forth in the executed CTA between the sponsor/CRO and the institution/investigator. The review is aimed at protecting the sponsor's proprietary information existing either at the date of the commencement of the study or generated during the study. The detailed obligations regarding the publication of any data, material results, or other information generated or created in relation to the study shall be set out in the agreement between each investigator and the sponsor or CRO, as appropriate.

11.10 Disclosure and Confidentiality

The contents of this protocol and any amendments and results obtained during the study should be kept confidential by the investigator, the investigator's staff, and the IRB/IEC and will not be disclosed in whole or in part to others, or used for any purpose other than reviewing or performing the study, without the written consent of the sponsor. No data collected as part of this study will be used in any written work, including publications, without the written consent of the sponsor. These obligations of confidentiality and non-use shall in no way diminish such obligations as set forth in either the Confidentiality Agreement or CTA executed between the sponsor/CRO and the institution/investigator. All persons assisting in the performance of this study must be bound by the obligations of confidentiality and non-use set forth in either the Confidentiality Agreement or CTA executed between the institution/investigator and the sponsor/CRO.

11.11 Discontinuation of Study

The sponsor reserves the right to discontinue the study for medical reasons or any other reason at any time. If a study is prematurely terminated or suspended, the sponsor will promptly inform the investigators/institutions and regulatory authorities of the termination or suspension and the reason(s) for the termination or suspension. The IRB/IEC will also be informed promptly and provided the reason(s) for the termination or suspension by the sponsor or by the investigator/institution, as specified by the applicable regulatory requirement(s).

The investigator reserves the right to discontinue the study should his/her judgment so dictate. If the investigator terminates or suspends a study without prior agreement of the sponsor, the investigator should inform the institution where applicable, and the investigator/institution should promptly inform the sponsor and the IRB/IEC and provide the sponsor and the IRB/IEC with a detailed written explanation of the termination or suspension. Study records must be retained as [noted above](#).

11.12 Subject Insurance and Indemnity

The sponsor will provide insurance for any subjects participating in the study in accordance with all applicable laws and regulations.

12 APPENDICES

Appendix 1 Sponsor's Grading for Laboratory Values

(revised per Amendment 01)

| | Grade 1 | Grade 2 | Grade 3 | Grade 4 |
|--|---|---|---|---|
| BLOOD/BONE MARROW | | | | |
| Hemoglobin (conversion from g/dL×0.6206) | Female (ULN=15.9 g/dL) <11.1 – 10.0 g/dL <111 – 100 g/L <6.9 – 6.2 mmol/L Male (ULN=17.7 g/dL) <12.6 – 10.0 g/dL <126 – 100 g/L <7.8 – 6.2 mmol/L | <10.0 – 8.0 g/dL <100 – 80 g/L <6.2 – 4.9 mmol/L | <8.0 g/dL <80 g/L <4.9 mmol/L; transfusion indicated | life-threatening consequences; urgent intervention indicated |
| Leukocytes (total white blood cell) | <3.40 – 3.0×10 ⁹ /L <3.40 10 ³ /uL – 3000/mm ³ (ULN=10.80 10 ³ /μL) | <3.0 – 2.0×10 ⁹ /L <3000 – 2000/mm ³ | <2.0 – 1.0×10 ⁹ /L <2000 – 1000/mm ³ | <1.0×10 ⁹ /L <1000/mm ³ |
| Lymphocytes | not applicable | <700 – 500/mm ³ <0.7 – 0.5×10 ⁹ /L | <500 – 200/mm ³ <0.5 – 0.2×10 ⁹ /L | <200/mm ³ <0.2×10 ⁹ /L |
| Neutrophils | not applicable | <1.4 – 1.0×10 ⁹ /L <1400 – 1000/mm ³ | <1.0 – 0.5×10 ⁹ /L <1000 – 500/mm ³ | <0.5×10 ⁹ /L <500/mm ³ |
| Platelets | <155 – 75.0×10 ⁹ /L <155 10 ³ /uL – 75,000/mm ³ (ULN=379 10 ³ /μL) | <75.0 – 50.0×10 ⁹ /L <75,000 – 50,000/mm ³ | <50.0 – 25.0×10 ⁹ /L <50,000 – 25,000/mm ³ | <25.0×10 ⁹ /L <25,000/mm ³ |
| METABOLIC/LABORATORY | | | | |
| Albumin, serum- low (hypoalbuminemia) | 2 - 59 years (ULN=5.5 g/dL) <3.5 – 3 g/dL <35 – 30 g/L 59 -69 years (LLN-ULN) <3.6 g/dL – 3 g/dL 69 -79 years (LLN-ULN) <3.5g/dL – 3g/dL 79 -89 years (LLN-ULN) <3.5g/dL – 3g/dL | <3 – 2 g/dL <30 – 20 g/L | <2 g/dL <20 g/L | life-threatening consequences; urgent intervention indicated |
| Alkaline phosphatase | Female: 18 -19 years >101 – 3.0×101 19 -61 years ULN=107 61 -71 years ULN=112 71 -150 years ULN=108 Male 18 -19 years >127 – 3.0×127 19 -61 years ULN=102 61 -71 years ULN=103 71 -150 years ULN=105 | >3.0 – 5.0×ULN See previous column for ULN values | >5.0 – 20.0×ULN See previous column for ULN values | >20.0×ULN See previous column for ULN values |
| Alanine aminotransferase | Female: >32 – 3.0×32 Male: >44 – 3.0 x 44 | Female: >3.0 – 5.0×32 Male >3.0 – 5.0×44 | Female: >5.0 – 20.0×32 Male: >5.0 – 20.0×44 | Female: >20.0×32 Male: >20.0×44 |

| | Grade 1 | Grade 2 | Grade 3 | Grade 4 |
|--|--|--|---|--|
| Aspartate aminotransferase | >40 – 3.0×40 | >3.0 – 5.0×40 | >5.0 – 20.0×40 | >20.0×40 |
| Bilirubin (hyperbilirubinemia) | >1.2 – 1.5×1.2 | >1.5 – 3.0×1.2 | >3.0 – 10.0×1.2 | >10.0×1.2 |
| Calcium, serum-low (hypocalcemia) (conversion to mmol×0.25) | <8.5 – 8.0 mg/dL <2.13 – 2.0 mmol/L | <8.0 – 7.0 mg/dL <2.0 – 1.75 mmol/L | <7.0 – 6.0 mg/dL <1.75 – 1.5 mmol/L | <6.0 mg/dL <1.5 mmol/L |
| Calcium, serum-high (hypercalcemia) | >10.6 – 11.5 mg/dL >2.65 – 2.9 mmol/L | >11.5 – 12.5 mg/dL >2.9 – 3.1 mmol/L | >12.5 – 13.5 mg/dL >3.1 – 3.4 mmol/L | >13.5 mg/dL >3.4 mmol/L |
| Cholesterol, serum-high (hypercholesterolemia) (conversion to mmol/L ×0.02586) | 0 -19 years >169 – 300 mg/dL >4.37 – 7.75 mmol/L 19 -150 years >199 – 300 mg/dL >5.15 – 7.75 mmol/L | >300 – 400 mg/dL >7.75 – 10.34 mmol/L | >400 – 500 mg/dL >10.34 – 12.92 mmol/L | >500 mg/dL >12.92 mmol/L |
| Creatinine | Female >1.00 mg/dL – 1.5×1.00 Male >1.27 mg/dL – 1.5×1.27 | Female >1.5 – 3.0×1.00 Male >1.5 mg/dL – 3.0×1.27 | Female >3.0 – 6.0×1.00 Male >3.0 mg/dL – 6.0 ×1.27 | Female >6.0×1.00 Male >6.0×1.27 |
| Gamma glutamyl transpeptidase | Female >60 IU/L – 3.0×60 Male >65 IU/L – 3.0×65 | Female >3.0 – 5.0×60 Male >3.0 – 5.0×65 | Female >5.0 – 20.0×60 Male >5.0 – 20.0×65 | Female >20.0×60 Male >20.0×65 |
| Glucose, serum-high (hyperglycemia) (conversion to mmol/L ×0.0555) | Fasting glucose value >99 – 160 mg/dL >5.5 – 8.9 mmol/L | Fasting glucose value >160 – 250 mg/dL >8.9 – 13.9 mmol/L | >250 – 500 mg/dL; >13.9 – 27.8 mmol/L; hospitalization indicated | >500 mg/dL; >27.8 mmol/L; life-threatening consequences |
| Glucose, serum-low (hypoglycemia) | <65 – 55 mg/dL <3.6 – 3.0 mmol/L | <55 – 40 mg/dL <3.0 – 2.2 mmol/L | <40 – 30 mg/dL <2.2 – 1.7 mmol/L | <30 mg/dL <1.7 mmol/L life-threatening consequences; seizures |
| Phosphate, serum-low (hypophosphatemia) (conversion to mmol/L ×0.323) | not applicable | <2.5 – 2.0 mg/dL <0.8 – 0.6 mmol/L | <2.0 – 1.0 mg/dL <0.6 – 0.3 mmol/L | <1.0 mg/dL <0.3 mmol/L life-threatening consequences |
| Potassium, serum-high (hyperkalemia) | not applicable | >5.5 – 6.0 mmol/L | >6.0 – 7.0 mmol/L hospitalization indicated | >7.0 mmol/L life-threatening consequences |
| Potassium, serum-low (hypokalemia) | <3.5 mEq/L – 3.0 mmol/L | <LLN – 3.0 mmol/L; symptomatic; intervention indicated | <3.0 – 2.5 mmol/L hospitalization indicated | <2.5 mmol/L life-threatening consequences |
| Sodium, serum-high (hypernatremia) | >144 mEq/L – 150 mmol/L | >150 – 155 mmol/L | >155 – 160 mmol/L hospitalization indicated | >160 mmol/L life-threatening consequences |
| Sodium, serum-low (hyponatremia) | <134 mEq/L – 130 mmol/L | Not applicable | <130 – 120 mmol/L | <120 mmol/L life-threatening consequences |
| Triglyceride, serum-high (hypertriglyceridemia) | 150 – 300 mg/dL 1.71 – 3.42 mmol/L | >300 – 500 mg/dL >3.42 – 5.7 mmol/L | >500 – 1000 mg/dL >5.7 – 11.4 mmol/L | >1000 mg/dL >11.4 mmol/L life-threatening consequences |

| | Grade 1 | Grade 2 | Grade 3 | Grade 4 |
|---------------------------------------|--|----------------|--|--|
| Uric acid, serum-high (hyperuricemia) | Female >7.1 – 10 mg/dL Male >8.6 – 10 mg/dL Both ≤0.59 mmol/L without physiologic consequences | Not applicable | Female >7.1 – 10 mg/dL Male >8.6 – 10 mg/dL Both ≤0.59 mmol/L without physiologic consequences | >10 mg/dL >0.59 mmol/L life-threatening consequences |

LLN = lower limit of normal, ULN = upper limit of normal.

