9.5.1.5.3 LABORATORY MEASUREMENTS

Clinical laboratory tests to be performed, including hematology, chemistry, urinalysis, and CSF are summarized in Table 4. Subjects should be in a seated or supine position during blood collection. Table 6 and Table 7 show the visits and time points at which blood for clinical laboratory tests and urine for urinalysis will be collected in the study.

See Section 9.3.3 for safety criteria for discontinuation from study drug related to absolute counts of CD4, CD8, and B lymphocytes, and for lymphocyte subset counts.

Table 4 Clinical Laboratory Tests

| Category | Parameters |
|-----------------------------|--|
| Hematology | Hematocrit, hemoglobin, platelets, red blood cell count, and white blood cell count with differential (bands, basophils, eosinophils, lymphocytes, monocytes, neutrophils). PT, PTT, and INR (Screening and Baseline only) (revised per Amendment 02) |
| Chemistry | |
| Electrolytes | Bicarbonate, calcium, chloride, phosphate, potassium, sodium |
| Liver function tests | Alanine aminotransferase, alkaline phosphatase, aspartate aminotransferase, gamma glutamyl transpeptidase, direct bilirubin, total bilirubin |

Table 4 Clinical Laboratory Tests

| Category | Parameters |
|-----------------------------|--|
| Renal function tests | Blood urea/blood urea nitrogen, creatinine |
| Other | Albumin, cholesterol, globulin, glucose, lactate dehydrogenase, total protein, triglycerides, uric acid |
| Urinalysis | Bacteria, casts, crystals, epithelial cells, glucose, ketones, occult blood, pH, protein, red blood cells, specific gravity, white blood cells |
| Other | Lymphocyte subset analyses (see Table 5). Regulatory T cells will be measured using CD4, CD25, and FoxP3 intracellular marker. PBMCs (revised per Amendment 02) Ig analyses (IgG, IgA, and IgM). Viral screen (HCVAb [Hepatitis C] and HBsAg [Hepatitis B]). Viral characterization (including HSV1, HSV2 and CMV, etc) Serum pregnancy test (females of child bearing potential only) Tuberculosis Interferon Gamma Release Assays Tests for thyroid function (thyroid stimulating hormone, free triiodothyronine and free thyroxine) and vitamin B12 Blood sample for storage for subsequent testing of immune status Cerebrospinal fluid sampling |

Whenever unscheduled lymphocyte subset tests are performed or whenever scheduled lymphocyte subsets are repeated, a CBC with differentials, must also be repeated. (revised per Amendment 02)

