9.7.1.8.3 LABORATORY VALUES

Laboratory results will be summarized using International System of Units, as appropriate. For all quantitative parameters listed in [Section 9.5.1.5.3](#), the actual value and the change from baseline to each postbaseline visit and to the end of treatment (defined as the last on-treatment value) will be summarized by visit and treatment group using descriptive statistics. Qualitative parameters listed in [Section 9.5.1.5.3](#) will be summarized using frequencies (number and percentage of subjects), and changes from baseline to each postbaseline visit and to end of treatment will be reported using shift tables. Percentages will be based on the number of subjects with both nonmissing baseline and relevant postbaseline results.

Laboratory test results will be assigned a low/normal/high (LNH) classification according to whether the value was below (L), within (N), or above (H) the laboratory parameter's reference range. Within-treatment comparisons for each laboratory parameter will be based on 3-by-3 tables (shift tables) that compare the baseline LNH classification to the LNH classification at each postbaseline visit and at the end of treatment. Similar shift tables will also compare the baseline LNH classification to the LNH classification for the highest and lowest value during the treatment period.

Appendix 1 (Sponsor's Grading for Laboratory Values) presents the criteria that will be used to identify subjects with treatment-emergent markedly abnormal laboratory values (TEMAVs). Except for phosphate, a TEMAV is defined as a postbaseline value with an increase from baseline to a Grade of 2 or higher. For phosphate, a TEMAV was defined as a postbaseline value with an increase from baseline to a Grade of 3 or higher. When displaying the incidence of TEMAVs, each subject may be counted once in the laboratory parameter high and in the laboratory parameter low categories, as applicable.

Lymphocyte subsets (ie, CD4 [T helper cells], CD8 [cytotoxic T cells], CD19 [B cells], CD16/CD56 [natural killer cells] and CD14 [macrophages]) and regulatory T cells will be summarized in the same manner as other laboratory parameters. Mean lymphocyte subsets and the mean change from baseline in lymphocyte subsets will also be displayed graphically over time by dose.

Serum IgG, IgM, and IgA will be measured and summarized in the same manner as other laboratory parameters.

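### Uric acid Grades 1 and 3 are defined identically in Appendix 1, so the protocol does not determine the count of markedly abnormal uric acid values

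*Protocol*

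**What the plan says.** Uric acid is a protocol chemistry test. Table 4 in Section 9.5.1.5.3 lists it in the group "Albumin, cholesterol, globulin, glucose, lactate dehydrogenase, total protein, triglycerides, uric acid".

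Section 9.7.1.8.3 gives Appendix 1 an operative role in the analysis: it "presents the criteria that will be used to identify subjects with treatment-emergent markedly abnormal laboratory values". The rule is: "Except for phosphate, a TEMAV is defined as a postbaseline value with an increase from baseline to a Grade of 2 or higher". Only one exception is made: "For phosphate, a TEMAV was defined as a postbaseline value with an increase from baseline to a Grade of 3 or higher". Uric acid has no exception.

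The uric acid row of Appendix 1 reads as follows:

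- Grade 1: "Female >7.1 – 10 mg/dL Male >8.6 – 10 mg/dL Both ≤0.59 mmol/L without physiologic consequences"
- Grade 2: not applicable
- Grade 3: the same text as Grade 1
- Grade 4: ">10 mg/dL >0.59 mmol/L life-threatening consequences"

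The order of the cells can be seen in the run "without physiologic consequences | Not applicable | Female >7.1 – 10 mg/dL", where the range begins again directly after the empty Grade 2.

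**The concern.** A grading table should place each result in at most one grade. Here two grades that are two steps apart have the same definition, and the TEMAV threshold falls between them. Because uric acid has no Grade 2, the Grade 3 cell alone decides whether any value at or below 10 mg/dL counts as a TEMAV, and that cell repeats Grade 1.

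Two programmers could follow the protocol faithfully and report different numbers. One would count only values above 10 mg/dL. The other would count every new value above the limit, including a woman at 7.2 mg/dL, and label it Grade 3. The shared qualifier also leaves a hole: a value in the range with physiologic consequences meets neither cell and is not above 10 mg/dL, so it has no grade.

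**Working it through.** No sample size, power or alpha figure is involved. The check applies the row and the TEMAV rule to test values.

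**Inputs.** Limits of 7.1 mg/dL (women) and 8.6 mg/dL (men), an upper bound of 10 mg/dL for Grades 1 and 3, and Grade 4 above 10 mg/dL, all from Appendix 1. The TEMAV threshold of Grade 2 or above comes from Section 9.7.1.8.3.

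**Step 1, compare the cells.** A character comparison of the Grade 1 and Grade 3 texts finds them identical, including the sex-specific limits, the mmol/L bound and the qualifier about physiologic consequences.

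**Step 2, apply the row.** The subject starts below the limit, so any grade reached is a rise. For Grade 4 only the numeric part of the cell is applied.

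| Value (mg/dL) | Women, no consequences | Men, no consequences | Either sex, with consequences |
|---|---|---|---|
| 7.0 | none | none | none |
| 7.2 | 1 and 3 | none | none |
| 8.5 | 1 and 3 | none | none |
| 8.7 | 1 and 3 | 1 and 3 | none |
| 9.5 | 1 and 3 | 1 and 3 | none |
| 10.0 | 1 and 3 | 1 and 3 | none |
| 10.1 | 4 | 4 | 4 |

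**Step 3, apply the TEMAV rule.** Grade 1 is below 2, so it is not a TEMAV. Grade 3 is at least 2, so it is. Every entry of 1 and 3 therefore gives both answers. A value of 10.1 gives a TEMAV under either reading.

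**Step 4, width of the affected range.** Women: 10 − 7.1 = 2.9 mg/dL. Men: 10 − 8.6 = 1.4 mg/dL.

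**Step 5, who is affected.** The ambiguity concerns subjects who move from below the limit into the range. A subject already in the range at baseline who stays there shows no rise if the same reading is used at both times. A subject who moves from the range to above 10 mg/dL rises to Grade 4 under either reading.

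**Step 6, compare with other rows.** High uric acid is not the only row without a Grade 2. Low sodium also has none, but its Grade 3 range (below 130 to 120 mmol/L) differs from its Grade 1 range (below 134 to 130). Low potassium uses the same lower bound of 3.0 mmol/L in Grades 1 and 2, but adds symptoms and a need for intervention to Grade 2. Uric acid is the only row in which two grades have the same text and nothing separates them.

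**The case against.** The duplication itself is hard to dispute. Grades 2 and 4 sit in their own cells around it, so a reading error from the PDF is unlikely, and the text is in the current appendix rather than the revision history. The case on the other side concerns weight and remedy, and most of it stands.

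- **Reach.** Section 9.7.1.8 says that safety is summarized descriptively. None of the discontinuation criteria in Section 9.3.3 uses uric acid. Section 9.7.1.8.3 also calls for actual values, changes from baseline and low/normal/high shift tables. These rest on measured values and reference ranges, not on Appendix 1 grades, so a difference in uric acid between arms could still be seen. This stands and keeps the point minor.
- **Scope.** A reader might infer that every newly high value up to 10 mg/dL receives two grades. The text does not support that, because both cells exclude values with physiologic consequences. Those values receive no grade.
- **Reporting.** A reader might also infer that every newly high subject will be reported as Grade 3. That would need a convention of taking the highest matching grade, which the protocol does not state.
- **Remedy.** Simply deleting the Grade 3 cell could remove an intended category, since the table elsewhere separates grades by a clinical qualifier. A slip in the Grade 3 qualifier is plausible but not shown. Nor can one assume that the central laboratory has its own uric acid criterion. The revision history names the analytes that were aligned with that laboratory, and uric acid is not among them.

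It could be said that the statistical analysis plan, which is not at hand, may settle the matter. But the protocol itself fixes both the table and the rule, and as written they contradict each other.

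**Conclusion.** The inconsistency is real and minor. For new values without physiologic consequences, above 7.1 and up to 10 mg/dL in women or above 8.6 and up to 10 mg/dL in men, the protocol gives both a TEMAV and a non-TEMAV. For the same values with such consequences it gives no grade. The uric acid TEMAV incidence by arm can therefore be either the values above 10 mg/dL alone, or those plus all new in-range values without consequences. The protocol does not choose between these.

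The number of subjects affected cannot be given, because the document has no uric acid distribution. The conclusion rests on the printed table and on the absence of any tie-break rule in the protocol. It does not extend to the other laboratory summaries, to treatment discontinuation or to any efficacy result.

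**What to change.** 1. Reconcile the two uric acid cells in Appendix 1 so that Grade 3 is distinct from Grade 1, and so that an in-range value with physiologic consequences has a defined grade. The sponsor must supply the intended Grade 3 criterion, because the protocol does not show it.
2. State for the TEMAV analysis that a uric acid value above the limit and up to 10 mg/dL, graded on the laboratory result alone, is Grade 1 and not a TEMAV.
3. State in the same place that values above 10 mg/dL count on the number alone. The Grade 4 cell also mentions life-threatening consequences, so this should not be left to interpretation.

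This concerns classification in the analysis only. The cost is one table cell, one or two sentences on the TEMAV rule and the matching line of programming. No additional data are needed for steps 2 and 3. The change should be made before safety summaries by arm are produced.
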